### **3.10.1 Screen failures**

Screening failures are patients who do not fulfil the eligibility criteria for the study, and therefore must not be randomized. These patients should have the reason for study withdrawal recorded as 'Incorrect Enrolment' (i.e., patient does not meet the required inclusion/exclusion criteria). This reason for study withdrawal is only valid for screen failures (not randomized patients).

### **3.10.2 Withdrawal of the informed consent**

Patients are free to withdraw from the study at any time (investigational product and assessments), without prejudice to further treatment.

A patient who withdraws consent will always be asked about the reason(s) and the presence of any adverse events (AE). The Investigator will follow up AEs outside of the clinical study. All unused study drug will be returned.

If a subject withdraws from participation in the study, then his/her enrolment/randomisation code cannot be reused. Withdrawn subjects will not be replaced.

## **3.11 Discontinuation of the study**

The study may be stopped if, in the judgment of the Sponsor, trial subjects are placed at undue risk because of clinically significant findings that:

- meet individual stopping criteria or are otherwise considered significant
- are assessed as causally related to study drug
- are not considered to be consistent with continuation of the study

Regardless of the reason for termination, all data available for the subject at the time of discontinuation of follow-up must be recorded in the CRF. All reasons for discontinuation of treatment must be documented.

In terminating the study, the Sponsor will ensure that adequate consideration is given to the protection of the subjects' interests.

## **4. STUDY PLAN AND TIMING OF PROCEDURES**

**Table 1** Study Plan detailing the procedures

Visit	1	2	3	4	5	6	7	8	Un-scheduled
Visit window	Screening	Baseline	2-week	3-month	6-month	9-month	12-month	2-4 week	Telephone follow-up
Days	-28 to 0 for Visit 1 ±14 day for Visit 3-7		Telephone follow-up		follow-up	follow-up	follow-up		AEs or SAEs
Months	0	0.5	3	6	9	12	12	12.5	
Written informed consent (including tissue samples, pharmacogenetics)	X								
Demographics	X								
Physical examination, height, and weight	X								
Medical/surgical history	X								
Inclusion/exclusion criteria	X	X							
Vital signs	X	X							
Randomisation to study treatment	X								
Treatment dispensed/returned	X				X	X	X		X
Concomitant medication	X	X	X	X	X	X	X	X	X
Adverse event review (AEs and SAEs)	X	X	X	X	X	X	X	X	X
Blood samples for haematology and clinical chemistry	X	X			X	X	X		X
Plasma sample storage								X	
Mit. F assessment								X	
Cardiac MRI scan*								X	

\*Cardiac MRI Scan may occur ±14 days from Baseline/12-Month clinical visit and data collection.

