### **3.7 Methods for unblinding**

Individual treatment codes, indicating the treatment randomisation for each randomised subject, will be available to the Investigator(s) or pharmacists at the study site, and the personnel who are independent to the study evaluation at the Sponsor.

The treatment code should not be broken except in medical emergencies when the appropriate management of the subject requires knowledge of the treatment randomisation. The Investigator documents and reports the action to Company, without revealing the treatment given to subject to the Company staff.

The Company retains the right to break the code for SAEs that are unexpected and are suspected to be causally related to an investigational product and that potentially require expedited reporting to regulatory authorities. Treatment codes will not be broken for the planned analyses of data until all decisions on the evaluability of the data from each individual subject have been made and documented.

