#### **4.2 Treatment period**

All eligible subjects will be randomized at 1:1 to Dapagliflozin 10mg or matching placebo orally once daily at baseline visit. We anticipate <10% of drop out from study enrollment to randomization. The treatment duration is at least 1 year. All study participants will be followed by telephone at 2 weeks and clinically every 3 months, a total of 4 follow-up visits. We will also perform a telephone visit at 2-4 weeks post the study completion to collect information on AE or SAE.

Following Randomization, Physician Randomization Letter will be sent to the subjects' physician(s) describing the study design, subject's participation, medication limitations and contact information for the study PI for any questions.

In the case of abnormal test results, we will contact healthcare providers by phone as soon as the results are available to inform them of the abnormal test results.

Additional glucose management, as needed, using any non-SGLT2 inhibitors or GLP-1 receptor agonists, will be allowed during the study.

In the event of a Public Health Emergency, such as COVID-19 Pandemic, MR service or Clinical space disruptions will be unavoidable. In this case, subjects will be invited to extend study treatment phase until a time that MR service or Clinical space disruptions have ended. This will allow study endpoint measures to coincide with the end of treatment. If treatment phase is extended, subjects will continue on randomized therapy with the same quarterly schedule described in Table 1 with procedures modelled on "3-Month follow-up" and "6-Month follow-up".

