# 8. STATISTICAL ANALYSES

## 8.1. Statistical considerations

- All personnel involved with the analysis of the study will remain blinded until database lock and protocol violators identified.
- Analyses will be performed by Principal Investigator or designees.

- Refer to Statistical Analysis Plan for details (if such a document exists and more details will be added).

A comprehensive Statistical Analysis Plan (SAP) will be prepared prior to first subject randomised and any subsequent amendments will be documented, with final amendments completed prior to unblinding of the data (this is the expectation for the pivotal studies).

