### **8.5.1. Analysis of the primary variable (s)**

Ancova test with adjusted for baseline GLS and ECV will be used to compare change in GLS and ECV over 12 months between 2 treatment groups.

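### The ±14-day MRI window runs to both sides of the Baseline visit, so a compliant baseline GLS or ECV may be measured on treatment

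*Combined protocol and SAP*

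**What the plan says.** The timing rule for the cardiac MRI is one footnote to Table 1 (Section 4): "Cardiac MRI Scan may occur ±14 days from Baseline/12-Month clinical visit and data collection". The same window, open on both sides, applies to the baseline and the 12-month scan. The version history (Version 4.0) explains that a window was needed because randomisation, MRI and the mitochondrial assay were hard to schedule for one day.

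Section 4.2 states that eligible subjects "will be randomized at 1:1 to Dapagliflozin 10mg or matching placebo orally once daily at baseline visit". Section 3.5 ties the randomisation scheme to dispensing by the investigational pharmacy. No section gives the date of first dose or orders it relative to the scan.

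Section 8.5.1 puts the baseline scan to work for both primary endpoints: "Ancova test with adjusted for baseline GLS and ECV will be used to compare change in GLS and ECV over 12 months". The efficacy set (Section 8.3.1) requires a scan at each of the two time points and that study drug or placebo was taken. It sets no condition on when the baseline scan was done. Section 8.5.5 marks sensitivity analysis as not applicable.

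Two blinded checks exist. Section 3.7 keeps treatment codes closed "until all decisions on the evaluability of the data from each individual subject have been made and documented", and Section 8.1 says that analysis personnel "will remain blinded until database lock and protocol violators identified".

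**The concern.** A baseline value should be free of any effect of the assigned treatment. Here a scan up to 14 days after randomisation still counts as baseline. In the dapagliflozin arm such a scan would carry whatever drug effect had appeared by then. A late scan in the placebo arm would carry none, so the two do not cancel. The contaminated value would enter the primary analysis twice, as the starting point of the change and as the covariate.

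If the early effect runs in the same direction as the 12-month effect, the treatment estimate is pulled towards zero. If it runs the other way, the estimate is inflated. The blinded checks are no safeguard as written: they have no scan-timing rule to apply, and a scan inside the window is not a protocol violation.

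**Working it through.** **Reading the text.** The window is anchored on the Baseline visit, and randomisation to daily treatment is at that visit. A compliant baseline scan can therefore fall on any of days 1 to 14 after randomisation; day 14 is also when Section 4.2 schedules the 2-week telephone call. For screening, Table 1 gives a window on one side only (day −28 to 0), so the table does fix order where order is intended. That dosing has begun by the time of a late scan is an inference: it follows if drug is started at or soon after the visit, which the text neither states nor rules out.

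**No plan figure to reproduce.** Section 8.2 says that no sample size calculation was possible. It gives no effect size, SD or rate of response. The inputs below are assumptions, apart from the 14 days, the treatment year (taken as 365 days) and 30 subjects per arm.

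**Formula.** Let δ be the true 12-month effect, *q* the share of dapagliflozin baseline scans done after first dose, *f* the fraction of δ already present at such a scan, and *b* the slope of the 12-month value on baseline.

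- Shift in the baseline difference between arms: *q f* δ.
- Difference in mean change: δ − *q f* δ.
- ANCOVA slope of change on baseline: *b* − 1.
- Adjusted effect: δ − *q f* δ − (*b* − 1) *q f* δ = δ(1 − *q f b*).

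The relative bias is thus *q* × *f* × *b*, towards zero when *f* is positive.

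**Values of *f*.** For exponential accrual with time constant τ, *f* at day 14 is (1 − exp(−14/τ)) / (1 − exp(−365/τ)).

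| Assumed accrual | *f* at day 14 | Mean *f* over days 0 to 14 |
|---|---|---|
| Linear over 365 days | 14/365 = 0.038 | 0.019 |
| Exponential, τ = 90 days | 0.147 | 0.075 |
| Exponential, τ = 30 days | 0.373 | 0.201 |

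**Relative bias with *b* = 0.6.**

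| *q* | Linear, late scans spread over days 0 to 14 | τ = 30 days, all late scans on day 14 |
|---|---|---|
| 0.10 | 0.10 × 0.0192 × 0.6 = 0.12% | 0.10 × 0.373 × 0.6 = 2.2% |
| 0.25 | 0.29% | 5.6% |
| 0.50 | 0.58% | 11.2% |

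With half the scans late but spread evenly, τ = 30 days gives 0.50 × 0.201 × 0.6 = 6.0%. In the bottom right cell, *b* from 0.4 to 0.8 moves the result from 7.5% to 14.9%.

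**Simulation.** ANCOVA on change was simulated with 30 per arm, *q* = 0.5, *b* = 0.6, an assumed effect of 0.72 residual SD and 8,000 runs. It gave −10.5% for *f* = 0.373 and +10.4% for *f* = −0.373 (Monte Carlo SE 0.4%), within about two Monte Carlo standard errors of the formula.

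**What a supportive analysis could show.** In residual SD units, the SE of the effect is √(2/30) = 0.26 with all subjects and √(2/15) = 0.37 if half are excluded, a ratio of √2 = 1.41. The difference between the full and the restricted estimate has SE √(2/15 − 2/30) = √(2/30) = 0.26. The largest bias in the table is 0.112 × 0.72 = 0.08 SD, about 0.3 of that SE. The restricted analysis could therefore not rule out a bias of this size.

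**The case against.** The strongest reply is that this is a gap in wording. The protocol calls the scan baseline throughout, which ordinarily means before treatment. The site may have scanned everyone before dosing. Section 8.1 also provides for a separate SAP, not among the supplied documents, where a baseline definition would normally sit. All of that is fair, and it limits the point to the supplied text. It does not remove it, because the footnote is a stated rule that allows the scan after the visit.

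A second reply is that the bias is small against the noise of a 60-subject study that its own synopsis calls exploratory. This also stands for most of the table, and it is why the point is an inexpensive improvement and not a fatal flaw.

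Three stronger readings are tempting and not supported.

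- A reader might infer that baseline scans were taken on treatment. The documents permit late scans; they do not show that any occurred.
- A reader might take 0.1% and 11% as best and worst cases. They are neither. The minimum is zero, if every scan precedes dosing, and other equally arbitrary inputs go higher: *f* = 0.25 with every dapagliflozin scan late and *b* = 0.7 gives 17.5%.
- A reader might infer that the same footnote contradicts Section 4.2 at the 12-month end, where it says "This will allow study endpoint measures to coincide with the end of treatment". That sentence describes only the extension for a public health emergency. Section 4.2 sets treatment at a year or longer, and nothing says that drug stops at the 12-month visit. A subject can still be on drug at a scan 14 days later, so the passages do not conflict.

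**Conclusion.** The point holds as a permitted risk. The supplied text lets a compliant baseline GLS or ECV be measured after treatment has begun, uses that value in the primary analysis, and has no timing rule to identify it. It depends on one inference, that dosing starts at or soon after the Baseline visit. The size and direction of the bias cannot be known from the documents, which give neither the speed of response of GLS or ECV nor the share of late scans. The illustrated range of about 0.1% to 11% of the effect rests on the assumed slope, accrual and lateness set out above. The correction is worth making because it costs little and because, without the timing data, a reader cannot tell whether baseline was pre-treatment.

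**What to change.** 1. Reword the Table 1 footnote so that the baseline MRI falls within the 14 days before, and no later than, first dose. Define baseline as the last scan before first dose.
2. For scans already done, derive the days from first dose to baseline scan during the blinded review, and tabulate them by arm at unblinding. Section 7.5 has drug administration recorded in the CRF and Section 9.4 has MRI data in the study database, so no new data collection should be needed. This table is the main safeguard.
3. Before unblinding, specify in Section 8.5.5 a supportive analysis that excludes post-dose baselines, and state that it is imprecise. Section 8.1 leaves room for this, since it foresees SAP changes "with final amendments completed prior to unblinding of the data".

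**Cost.** Item 1 gives up some of the scheduling flexibility for which the window was introduced. It could also mean contrast scans in subjects who are never randomised. Section 4.2 says "We anticipate <10% of drop out from study enrollment to randomization", so for 60 randomised the number is below 60/0.9 − 60 = 6.7, that is, fewer than 7, even if every such subject had been scanned. Item 1 may reach few remaining scans, because Section 9.3 plans the study to end in March 2021 and Version 8.0 is dated July 2022. Items 2 and 3 need only dates. If half the scans were late, item 3 would raise the SE by about 41%, so it must remain supportive.

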#### **4.1 Enrolment/screening period**

With IRB approval, potential qualified subjects will be identified using patient electronic medical records system at the University of Washington. Subjects who appear to meet the study entry requirement will be invited for participating in the screening visit.

At screening, consenting subjects are assessed to ensure that they meet eligibility criteria. Subjects who do not meet these criteria must not be enrolled in the study.

Following Screening, a Physician Introduction Notification Letter will notify that the subject is considering participation once subject has consented and authorized discussion.

For the Mit. F study, 30 age, gender and CVD risk matched non-diabetic subjects will be included ONLY for baseline monocytes Mit. F assessment.

#### **4.2 Treatment period**

All eligible subjects will be randomized at 1:1 to Dapagliflozin 10mg or matching placebo orally once daily at baseline visit. We anticipate <10% of drop out from study enrollment to randomization. The treatment duration is at least 1 year. All study participants will be followed by telephone at 2 weeks and clinically every 3 months, a total of 4 follow-up visits. We will also perform a telephone visit at 2-4 weeks post the study completion to collect information on AE or SAE.

Following Randomization, Physician Randomization Letter will be sent to the subjects' physician(s) describing the study design, subject's participation, medication limitations and contact information for the study PI for any questions.

In the case of abnormal test results, we will contact healthcare providers by phone as soon as the results are available to inform them of the abnormal test results.

Additional glucose management, as needed, using any non-SGLT2 inhibitors or GLP-1 receptor agonists, will be allowed during the study.

In the event of a Public Health Emergency, such as COVID-19 Pandemic, MR service or Clinical space disruptions will be unavoidable. In this case, subjects will be invited to extend study treatment phase until a time that MR service or Clinical space disruptions have ended. This will allow study endpoint measures to coincide with the end of treatment. If treatment phase is extended, subjects will continue on randomized therapy with the same quarterly schedule described in Table 1 with procedures modelled on "3-Month follow-up" and "6-Month follow-up".

#### **4.3 Follow-up period**

Same as in 4.2.

In addition, Physician Exit Letter will be sent to notify the subjects' physician(s) of study exit to explicitly indicate that the study drug/placebo has been stopped.

## 5. STUDY ASSESSMENTS

The Investigator will ensure that data are recorded on the paper Case Report Forms and are recorded in an electronic database.

The Investigator ensures the accuracy, completeness, legibility and timeliness of the data recorded and of the provision of answers to data queries according to the Research Agreement.

The Principal Investigator/Investigator will record data on the observations, tests and assessments specified in the protocol on the paper CRFs provided by Sponsor. The CRF will be accompanied with 'Instructions for the Investigator', which should be followed. These instructions provide guidance for the recording of study data in the CRF including how to change data incorrectly recorded.

### 5.1 Efficacy assessments

Subjects will be scanned on a Philips Achieva 3T scanner at the University of Washington. Cardiac coils will be applied in the scan session. There will be pre-contrast and post-contrast scans. ECG leads will be placed on the subject to obtain cardiac gating signal for the cardiac scans. Subject will be instructed to hold their breath in end-expiratory position for breath-hold scans.

The heart will be identified using 3-plane gradient echo scan followed by additional planes to identify the short axis. A pre-contrast T1 mapping scan (MOLLI) will be obtained at a single location oriented in the short axis scan plane of the heart. Next gadolinium contrast bolus will be injected intravenously at a dose of 0.05 mmol/kg using a power injector at the rate of 1ml/sec. Then a 3D phase-sensitive inversion recovery (3D PSIR) of the heart will be obtained followed by a post-contrast MOLLI T1 mapping scan and T2 mapping scan. Total scan time for the protocol is <1 hour including patient setup time.

**Myocardial strain measurements** with feature tracking will be performed using Circle Cardiovascular Software (cv42, Circle Cardiovascular Imaging Inc., Calgary, Alberta, Canada) to measure myocardial strain and strain rate from the bSSFP short-axis and long-axis cine images. Long-axis cine images will be further used to compute global myocardial longitudinal strain (GLS). Short-axis images will be used to compute circumferential (GCS) and radial strain (GRS) and strain rate. The global values will be obtained through averaging the values according to an AHA 17-segment model [38].

**Quantitative measurements of Extracellular Volume Fraction (ECV), the primary study measure**, will be performed using MASS research software (Department of Radiology,

Leiden University Medical Center, Leiden, the Netherlands). T1 maps will be constructed offline. On each T1 map (pre- and post-contrast), a region of interest will be manually drawn around the core myocardium to exclude the blood pool and epicardial fat to calculate the myocardial T1 time for each subject. The partition coefficient will be determined by the slope of the linear relationship of (1/T1myo vs. 1/T1blood). If the change of 1/T1myo and 1/T1blood is expressed as  $\Delta R1_{myo}$  and  $\Delta R1_{blood}$ , fraction of extracellular volume (ECV [%]) will be derived using the formula: ECV =  $\Delta R1_{myo} / \Delta R1_{blood} \times (1 - \text{hematocrit})$ .

PBMC monocyte oxygen consumption rates (OCR) will be assessed at the mitochondrial research center of the University of Washington using the established methods [31].

## 5.2 Laboratory assessments

### 5.2.1 Laboratory assessments

The following laboratory variables will be measured. Fasting glucose, creatinine, and HbA1C will be measured at every 3 months and other variables will be assessed at every 6 months.

**Table 2** Laboratory Variables

Whole blood	Clinical Chemistry (serum or plasma)
HbA1C	S/P-Creatinine
	S/P-Fasting glucose
Clinical Chemistry (serum or plasma)	S/P-Alkaline phosphatase (ALP)
S/P-Total cholesterol	S/P-Aspartate transaminase (AST)
S/P-Triglycerides	S/P-Alanine transaminase (ALT)
S/P-LDL cholesterol	S/P-Albumin
S/P-HDL cholesterol	S/P-Potassium
S/P-Total cholesterol	S/P-Calcium, total
S/P-Creatine kinase (CK)	S/P-Sodium
S/P-ProBNP	S/P-HsCRP
S/P-Uric acid	Urinalysis
S/P-Potassium	Pregnancy test

### 5.2.2 Physical examination

A targeted physical examination will be performed at baseline and 12-month follow-up visits and at any visits related to AEs. It will include an assessment of the following: general appearance, respiratory, cardiovascular, abdomen and lower extremities.

### **5.2.3 ECG**

Not required for the study.

#### **5.2.3.1 Resting 12-lead ECG**

Not required for the study.

### **5.2.4 Vital signs**

#### **5.2.4.1 Pulse and blood pressure**

Pulse and blood pressure will be taken at each of the clinical visits at screening, baseline/randomization, 3-month, 6-month, 9-month and 12-month follow-up visits. These measures will be taken at sitting position after 15 minutes of resting. They will be an average of 2 readings 5 minutes apart.

#### **5.2.4.2 Body temperature**

It will be taken at each of the clinical visits at screening, baseline/randomization, 3-month, 6-month, 9-month and 12-month follow-up visits.

### **5.2.5 Other safety assessments**

Body weight in Kg will be assessed at each of the clinical visits at screening, baseline/randomization, 3-month, 6-month, 9-month and 12-month follow-up visits.

## **5.3 Other assessments**

### **5.3.1 Patient reported outcomes**

Only adverse events reported by the study participants will be recorded using an AEs log.

## **5.4 Pharmacokinetics**

### **5.4.1 Collection of samples**

Pharmacokinetic samples will not be taken during the study.

### **5.4.2 Determination of drug concentration**

Drug concentration will not be assessed in this study.

